16.2.1.9. Change from baseline PGIS at each post-baseline visit

The Patient Global Impression of Severity (PGIS) comprises two questions:

- o severity of your EoE symptoms over the past 7 days
- o severity of your difficulty with food or pills going down over the past 7 days
- For each question, subjects can answer:
- o None
- o Mild
- Moderate
- o Severe
- Very Severe.
- This information will be retrieved from the daily diary;

16.2.1.10. PGIC at each post-baseline visit 52

The Patient Global Impression of Change (PGIC) comprises the same two questions as the PGIS (see section 16.2.1.9):

- o severity of your EoE symptoms
- o severity of your difficulty with food or pills going down

with subjects assessing themselves relative to before starting study treatment.

PGIC responses at each post-baseline visit will be one of

- Much worse
- Moderately worse
- A little worse
- Stayed the same

Author:

Version Number: 3.0

Version Date: 06NOV2019

Template No.: CS_TP_BS016 Revision 5 Reference: CS_WI_BS005

Page 43 of 70

- A little improved
- Moderately improved
 - o Much improved.
 - o This information will be retrieved from the daily diary;

16.2.1.11. Assessment of treatment failure and relapse, including

Percentage of histologic non-responders at Week 12, Week 26, and Week 52

Histologic non-responders are subjects who do not achieve \leq 6 peak eosinophils/HPF after assessment of at least 5-6 biopsies from the proximal and distal esophagus (\sim 3 each) where the HPF area is 235 square microns (40 magnification lens with a 22 mm ocular).

For each visit, subjects who have withdrawn from the study prior to the visit are classified as non-responders at that visit.

- Percentage of subjects requiring emergency endoscopic food dis-impaction by dose before Week 14, between Week 14 and Week 28, and between Week 28 and Week 52 – retrieved from EGD assessment before unscheduled visit
- Percentage of subjects requiring esophageal dilation by dosing group and part of the study retrieved from EGD assessment before unscheduled visit

16.2.2. MISSING DATA METHODS FOR SECONDARY EFFICACY VARIABLES

Subjects who did not complete Week 26 histological assessment will be classified as Week 26 non-responders. Subjects who were non-responders at Week 26 are to be withdrawn from the study at Week 26. These subjects and any subjects who either terminated the study early or did not completed Week 52 histological assessment will be counted as non-responders at Week 52.

Visitwise missing data will not be imputed in summaries or analyses of exploratory variables.

Rules for imputing missing data for the derivation of other individual parameters prior to summarizing or analyzing the variable, are provided in the relevant sections Error! Reference source not found. through to Error!

Reference source not found..

Author:

Version Number: 3.0

Version Date: 06NOV2019

Template No.: CS_TP_BS016 Revision 5 Reference: CS_WI_BS005

Page 44 of 70

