## 4.0 INVESTIGATIONAL PLAN

# 4.1 Summary of Study Design

FLUTE is a randomized, double-blind, placebo-controlled dose-ranging study of 4 total daily doses of APT-1011 versus placebo in 100 adult subjects (≥18 years of age) diagnosed with EoE. During the single-blind run-in/baseline symptom assessment, the subjects will receive placebo 30 minutes after breakfast and HS (at bedtime). APT-1011 will be administered in 4 doses: Placebo 30 minutes after breakfast and 1.5 mg HS (at bedtime), 1.5 mg BID (30 minutes after breakfast and at bedtime; total daily dose of 3 mg), 3 mg HS (at bedtime), and 3 mg BID (30 minutes after breakfast and at bedtime; total daily dose of 6 mg), compared with matching placebo administered 30 minutes after breakfast and HS (at bedtime). The randomization scheme is discussed in Section 4.1.5.2. Efficacy (histological response), safety, and PK of APT-1011 will be examined.

FLUTE will enroll around 100 adult ( $\geq$ 18 years of age) subjects (see Section 8.1 for a discussion of the potential number of subjects to participate in each part).

FLUTE is planned to be performed at approximately 60 active sites in North America (US and Canada) and Western Europe (Belgium, Germany, Switzerland and Spain).

The study will be conducted in several parts (Screening, 4-week single-blind placebo run-in and Baseline Symptom Assessment, and 2 treatment parts [Part 1 and Part 2]) with a Follow-up Visit to occur 2 weeks after the final dose of study drug.

Subjects who enter and complete FLUTE will be in the study for up to 62 weeks or until the last subject completes Week 28.

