3. STUDY DESIGN

3.1. GENERAL DESCRIPTION

FLUTE is a randomized, double-blind, placebo-controlled dose-ranging study of 4 total daily doses of APT 1011 versus placebo in 100 adult subjects (≥18 years of age) diagnosed with EoE.

The study will be conducted in several parts (Screening, 4-week single-blind placebo run-in and Baseline Symptom Assessment, and 2 treatment parts [Part 1 and Part 2]) with a Follow up Visit to occur 2 weeks after the final dose of study drug.

During the single-blind run-in/baseline symptom assessment, the subjects will receive placebo 30 minutes after breakfast and HS (at bedtime). At the end of the run-in period eligible subjects will be randomized to one of 4 doses of APT-1011 or placebo in a 1:1:1:1:1 ratio. Randomization will occur via an integrated Interactive Web Response System (IWRS), and will be stratified by the presence or absence of a history of or current esophageal stricture at Screening and history of a prior positive steroid response to any corticosteroid treatment previously received to treat the subject's EoE.

APT-1011 will be administered in 4 doses:

- 1.5 mg HS: Placebo 30 minutes after breakfast and 1.5 mg HS (at bedtime)
- 1.5 mg BID (1.5 mg 30 minutes after breakfast and at bedtime; total daily dose of 3 mg)
- 3 mg HS (Placebo 30 minutes after breakfast and 3.0 mg at bedtime)
- 3 mg BID (3.0 mg 30 minutes after breakfast and at bedtime; total daily dose of 6 mg)

Page 12 of 70

Subjects randomized to placebo will receive matching placebo administered 30 minutes after breakfast and HS (at bedtime).

Efficacy (primary efficacy of histological response), safety, and PK of APT 1011 will be examined.

A histological assessment will be performed at Week 12, and non-responders to treatment will receive single-blind (to the subject) APT-1011 3.0 mg BID after Week 14, the end of Part 1 of the study. Part 2 of the study continues until Week 52. Subjects who are histological non-responders at Week 26 are to be withdrawn from the study at that time.

FLUTE is planned to be performed at approximately 60 active sites in North America (US and Canada) and Western Europe (Belgium, Germany, Switzerland and Spain).

Subjects who enter and complete FLUTE will be in the study for up to 62 weeks or until the last subject completes Week 28.

A study schematic is provided in Figure A.

Document:

Author: Version Number: 3.0

Version Date: 06NOV2019

Template No.: CS_TP_BS016 Revision 5 Reference: CS_WI_BS005

Page 13 of 70

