3.0

06NOV2019

Figure A Study Schematic Table A: PHASE 2: SP-1011-002 Part 1 (14 week induction) Part 2 Maintenance (Weeks 14 to up to Week 52) **EGD** EGD Wk-12 Wk-26 and Wk-52 1.5 mg HS 1.5 mg HS Screening 4 wk+ 2- week run-in/baseline Follow-up 1.5 mg BID 1.5 mg BID symptom assessment period 4 wk 3.0 mg HS 3.0 mg HS N=100 STUDY and Randomization 1:1:1:1:1 3.0 mg BID FINALIZE: 3.0 mg BID Dose effectiveness Placebo Placebo registration study PHASE 2: Response to Primary endpoint: Responders ≤6 higher dose eosinophils/HPF in induction Secondary endpoint: EREFS, Symptom anchor scales (PGI-S, PGI-C), Reduction in Non-Responders responders dysphagia episodes over previous 14 days Key: (based upon new PRO questionnaire) Single Blind (to patient): 3.0 Mg BID response No response Document:

Template No.: CS_TP_BS016 Revision 5

Reference: CS_WI_BS005

Effective Date: 01Apr2018

Author:

Copyright © 2009, 2010, 2012, 2016, 2018 IQVIA. All rights reserved. The contents of this document are confidential and proprietary to IQVIA Holdings Inc. and its subsidiaries. Unauthorized use, disclosure or reproduction is strictly prohibited.

Version Number:

Version Date:

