6.3. DERIVED TIMEPOINTS

There will be no derived timepoints in this study. EOT visits will be recorded separately and will not be re-mapped.

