6.5. WINDOWING CONVENTIONS

No windowing or mapping of visits will be conducted. Visits will be included as they are recorded by the site, regardless of study day.

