16.2. SECONDARY EFFICACY

16.2.1. SECONDARY EFFICACY VARIABLES & DERIVATIONS

16.2.1.1. EoE sustained response: maintenance of ≤6 peak eosinophils/HPF at Weeks 26 and 52 for histologic responders at Week 12

For histologic responders at Week 12, maintenance of ≤ 6 peak eosinophils/HPF at each of Week 26 and Week 52 is defined as having ≤ 6 peak eosinophils/HPF (as per the primary efficacy variable in section 16.1.1), at each of Weeks 26 and 52 respectively.

Subjects who withdrew prior to each of Weeks 26 and 52 will be classified as non-responders at those visits.

Author:

Version Number: 3.0

Version Date: 06NOV2019

Template No.: CS_TP_BS016 Revision 5 Reference: CS_WI_BS005

Page 37 of 70

16.2.1.2. Change from baseline EREFs Total Score at Week 12, Week 26, and Week 52 For total esophagus:

- each of edema and stricture will be classified as either Grade 0 (absent) or Grade 1 (present)
- rings will be classified as Grade 0 (none), Grade 1 (mild), Grade 2 (moderate), Grade 3 (severe)
- each of exudates and furrows will be classified as Grade 0 (none), Grade 1 (mild), Grade 2 (severe)

Crepe paper esophagus and narrow caliber esophagus will each be classified as Grade 0 (absent) or Grade 1 (present).

Esophageal erosions will be classified as Normal, and each of Grade A through to Grade D based on the Los Angeles Classification, but not separately for the proximal and distal esophagus.

A total EREFs score will be derived as follows:

Component	Grade	Score
Edema*	Absent	0
	Present	1
Rings*	Grade 0 (none)	0
	Grade 1 (mild)	1
	Grade 2 (moderate)	2
	Grade 3 (severe)	3
Exudates*	Grade 0 (none)	0
	Grade 1 (mild)	1
	Grade 2 (severe)	2
Furrows*	Grade 0 (none)	0
	Grade 1 (mild)	1
	Grade 2 (severe)	2
Stricture*	Absent	0
	Present	1

Author:

Version Number: 3.0

Version Date: 06NOV2019

Template No.: CS_TP_BS016 Revision 5 Reference: CS_WI_BS005

Page 38 of 70

Crepe paper esophagus	None	0
	Present	1
Narrow caliber esophagus	None	0
	Present	1
Esophageal erosions (Los Angeles	Normal	0
Classification)	Grade A	1
	Grade B	2
	Grade C	3
	Grade D	4
Total score		Sum of the above (ranging from 0
		to 15)

- * For this component the grade/score will be based on the WORST result.

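### If the study closes at the last subject's Week 28, SAP 16.2.2 scores responders who could not yet reach Week 52 as Week 52 non-responders; the study-end rule and the Week 52 rule both need one clear wording

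*SAP*

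**What the plan says.** **Length of participation.** Protocol 4.1 says subjects who enter and complete the trial will be "in the study for up to 62 weeks or until the last subject completes Week 28". SAP 3.1 repeats it: "Subjects who enter and complete FLUTE will be in the study for up to 62 weeks or until the last subject completes Week 28". Neither says whether the earlier or the later limit applies. SAP Figure A labels the second part "Part 2 Maintenance (Weeks 14 to up to Week 52".

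**Subjects without Week 52 histology.** SAP 16.2.2 covers Week 26 non-responders, who have already stopped, and then adds that "any subjects who either terminated the study early or did not completed Week 52 histological assessment will be counted as non-responders at Week 52". The reason for the missing biopsy does not matter.

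**The endpoint sections.** SAP 16.2.1.1, on sustained response, says: "Subjects who withdrew prior to each of Weeks 26 and 52 will be classified as non-responders at those visits". SAP 16.2.1.11, on the percentage of non-responders, says: "For each visit, subjects who have withdrawn from the study prior to the visit are classified as non-responders at that visit". Both mention withdrawal and no other reason.

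**Denominator.** SAP 16.2.3.1 includes Week 12 histologic responders only. Protocol 8.8.2 instead assesses Week 52 sustained response in subjects who complete the Week 52 evaluations. SAP 3.3, which lists changes from the protocol, does not mention this one.

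**Exit biopsies.** SAP 6.3 says "EOT visits will be recorded separately and will not be re-mapped", and SAP 6.5 says "No windowing or mapping of visits will be conducted".

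**Planning counts.** Protocol 8.1.1 expects about 42 responders to complete Week 26 and about 34 of them to complete Week 52.

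**The concern.** Maintenance of efficacy is a named secondary objective, and the sustained-response table is its Week 52 evidence. If the trial closes once the last subject has completed Week 28, anyone randomised less than 24 weeks before that subject cannot have a Week 52 biopsy. Week 26 non-responders stop at Week 28 (protocol 4.1.6.2). The subjects cut off after that point who have not withdrawn are therefore Week 26 responders still on study drug. Under SAP 16.2.2 they would enter the table as failures for a purely administrative reason. The reported rate would be too low, and would depend partly on when subjects were randomised.

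The wording is also not uniform for any subject who lacks a Week 52 biopsy but did not withdraw. That includes a subject who stays in the study and misses the Week 52 endoscopy, so harmonising the text is worthwhile on either reading of the study-end clause.

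**Working it through.** **1. What the study-end clause can mean.** Screening 4 + run-in 4 + treatment 52 + follow-up 2 = 62 weeks. The first limb is thus the whole schedule. Read as whichever is later, the second limb would have nothing to govern, because the schedule of events has no visit after Week 52 except the Follow-up Visit. Read as whichever is earlier, it ends participation before Week 52 for late entrants. SAP 4 runs the final analysis when all subjects have exited or completed, without requiring that all reach Week 52. The follow-up triggers (protocol 4.1.8) and discontinuation reasons (protocol 4.2.3) name no study-end exit. The evidence against early closure is set out under the objection.

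**2. Who would be affected.** Subjects randomised less than 52 − 28 = 24 weeks before the last subject. With even accrual over T weeks, their share is 24/T. T is not in the documents; 52, 78 and 104 weeks are assumptions.

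**3. Starting rate.** Protocol 8.1.1 assumes 20% loss among responders by Week 26 and 20% of the remainder by Week 52, so 0.8 × 0.8 = 64% of Week 12 responders sustained. The protocol's own pair gives 34/42 = 81%. Neither allows for histologic relapse.

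**4. Rate reported under SAP 16.2.2** = starting rate × (1 − 24/T).

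| Assumed accrual | Share cut off | 64% reads | 81% reads | Week 12 responders who could reach Week 52 (of 42) | Same, per higher-dose arm (of 12) |
|---|---|---|---|---|---|
| 52 weeks | 24/52 = 46% | 34% | 44% | 22.6 | 6.5 |
| 78 weeks | 24/78 = 31% | 44% | 56% | 29.1 | 8.3 |
| 104 weeks | 24/104 = 23% | 49% | 62% | 32.3 | 9.2 |

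From 64%, the bias is about −30, −20 and −15 points. With the denominator limited by randomisation date, the expected rate stays at its starting value.

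**5. An exit biopsy would not rescue these subjects.** Protocol 4.1.8 asks for a final endoscopy within three weeks before the Follow-up Visit, but SAP 6.3 and 6.5 do not allow that result to be mapped to Week 52.

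**6. The same biopsy schedule, treated differently elsewhere.** For peak counts below 1 and below 15, SAP 16.2.1.3 and 16.2.3.3 leave subjects without an assessment out of the denominator. A subject cut off by closure would be a failure in one Week 52 histology table and absent from another.

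**7. Planning counts in protocol 8.1.1.** The second figure follows from the first: 42 × 0.8 = 33.6, or about 34. The first does not follow from the listed steps:

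- Week 12 responders: 20 × (3 × 0.6 + 0.2 + 0.1) = 42.
- After the stated 20% loss by Week 26: 42 × 0.8 = 33.6. After a further 20% by Week 52: 26.9.
- If 60% of the 58 Part 1 non-responders convert: 58 × 0.6 = 34.8. Week 26 total: 33.6 + 34.8 = 68.4. Week 52: 68.4 × 0.8 = 54.7.

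**The case against.** The strongest objection is that the trial may never be cut short. Protocol 2.5.1 says Week 26 responders continue on the same dose until Week 52. Protocol 4.1.6.2 treats them up to Week 52 and speaks of subjects who complete the study at Week 52. Protocol 8.1.1 plans for only 20% loss after Week 26, with no allowance for administrative cut-off. The wording in Figure A is weak support for early closure, since Week 26 non-responders stop at Week 28 and that alone explains it. All of this stands. It makes the point conditional; it does not remove the ambiguity in a sentence that both documents carry.

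Second, a reader might infer that SAP 16.2.1.1 and 16.2.1.11 contradict 16.2.2 outright. The documents do not support that. Neither section restricts non-response to withdrawals. Both start from attaining the histologic threshold, which a subject with no biopsy has not done, and their withdrawal sentences can be read as a subset of the general rule. What stands is that the wording is not uniform.

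Third, SAP 16.2.3.1 already fixes the denominator as Week 12 responders, so the conflict with protocol 8.8.2 is largely settled. The unlisted departure remains.

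Fourth, non-responder imputation is conservative for efficacy and matches the primary analysis. That is sound for withdrawals and failures. It is less apt for subjects whose follow-up the sponsor ended.

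Finally, the magnitudes rest on assumed accrual and an assumed starting rate. They illustrate direction and scale and are not estimates for this trial.

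**Conclusion.** The point holds conditionally and should be settled before final lock. If the clause shortens participation, SAP 16.2.2 as written biases the Week 52 maintenance rate downward. Under the assumed accrual periods the shortfall is roughly 15 to 30 points from a 64% start. If nobody is cut off, it is zero.

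The reach is limited. Part 2 is descriptive and this table carries no test, so Type I error, the Week 12 primary analysis and its power are untouched. Week 26 is unaffected, because every subject can reach Week 28. A reader might infer that comparisons between doses are distorted. The documents give no basis for that: randomisation is concurrent across arms, and nothing suggests that late entry differs by dose.

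The planning count in protocol 8.1.1 is a separate and smaller error. The 42 is the Week 12 figure, and the correct replacement depends on whether converting Part 1 non-responders are meant to be counted.

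**What to change.** 1. State whether the Week 28 clause shortens participation, and reconcile Protocol 4.1 and SAP 3.1 with Protocol 2.5.1, 4.1.6.2 and 8.1.1.
2. If it does, limit the Week 52 denominator to Week 12 responders whose randomisation date allowed them to reach Week 52 before study end. Select by date alone, so that late-randomised failures leave along with late-randomised responders. Within that set, keep non-responder imputation for withdrawal, treatment failure, Week 26 non-response and a missed Week 52 biopsy.
3. Use one wording in SAP 16.2.1.1, 16.2.1.11 and 16.2.2, and list the departure from protocol 8.8.2 in SAP 3.3.
4. Correct protocol 8.1.1 to about 34 (Week 26) and 27 (Week 52) among Part 1 responders, or about 68 and 55 if converting Part 1 non-responders are counted, and say which is meant.

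The cost is wording, plus randomisation and study-end dates that are already held. The downside is a smaller Week 52 denominator: about 23 to 32 of the 42 expected Week 12 responders under the assumed accrual periods. In a higher-dose arm the approximate 90% half-width, 1.645 × √(0.64 × 0.36/n), would widen from 23 points at n = 12 to 31, 27 or 26 points at n = 6.5, 8.3 or 9.2. For accrual of 52, 78 or 104 weeks that is a loss of 8, 4 or 3 points of precision, against a bias of 30, 20 or 15 points removed. In the placebo arm, with 2 expected responders, the date limit brings no comparable gain in overall accuracy.

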16.2.3. Analysis of Secondary Efficacy Variables

Statistical tests to compare each APT-1011 dosing group with placebo will be performed for some secondary efficacy endpoints as described in the following sections, but the corresponding p-values will be considered as descriptive rather than inferential. The analyses and summaries of secondary efficacy variables will be performed for FAS analysis set.

16.2.3.1. Analysis of EoE sustained response: maintenance of ≤6 peak eosinophils/HPF at Weeks 26 and 52 for histologic responders at Week 12

The frequency and percentage of histologic responders at Week 12 who maintained response at each of Week 26 and Week 52 will be provided for each randomized dosing group. Only histologic responders at Week 12 will be included in the summary.

No statistical testing will be performed.

16.2.3.2. Analysis of change from baseline PGIS and change from baseline in each of the EEsAI items trouble swallowing, duration of trouble swallowing and pain when swallowing

For each of the two PGIS questions (see section 16.2.1.9) and for the EEsAI items trouble swallowing frequency, duration of trouble swallowing and pain when swallowing, shift tables will be provided for the results at baseline and at each post-baseline visit, for each randomized dosing group. Data will not be not included for visits after a histologic non-responder at Week 12 had received single-blind (to subject) APT-1011 3 mg BID in Part 2.

No statistical testing will be performed.

16.2.3.3. Analysis of percentage of subjects with a peak eosinophils/HPF number <1 and <15 and percentage of subjects with 7-day EEsAI total score <20

The number and percentage of subjects in each of these categories will be presented by visit for each of the randomized dosing groups.

The summaries will only include data while subjects are receiving double-blind study drug. Data will not be included for visits after a histologic non-responder at Week 12 had received single-blind (to subject) APT-1011 3 mg BID in Part 2.

Patients who do not have assessments at the respective visits will not be included in the denominator for

Author:

Version Number: 3.0

Version Date: 06NOV2019

Template No.: CS TP BS016 Revision 5

Reference: CS WI BS005

Effective Date: 01Apr2018

Copyright © 2009, 2010, 2012, 2016, 2018 IQVIA. All rights reserved. The contents of this document are confidential and proprietary to IQVIA Holdings Inc. and its subsidiaries. Unauthorized use, disclosure or reproduction is strictly proh bited.

Page 45 of 70

percentages.

No statistical testing will be performed.

16.2.3.4. Analysis of Change from baseline in each of Global EoE Symptom Score, Total EREFs Score, Number of Dysphagia Episodes, 7-day EEsAI total score, 7-day EEsAI VDQ and AMS subscores The change from baseline in each of Global EoE Symptom Score (see section 16.2.1.4), 7-day EEsAI total score (see section 16.2.1.6) and 7-day EEsAI VDQ and AMS subscores (see section 16.2.1.7) will be summarized as continuous variables, and analysis of covariance (ANCOVA) will be used to compare the mean change from baseline in each of the APT-1011 dosing groups to placebo, at the Week 12 visit, with the estimated mean difference, 90% confidence interval of the mean difference and 1-sided p-values provided. This statistical testing at Week 12 is considered descriptive only and no adjustments will be made for multiple comparisons. The ANCOVA models will include the factors described in section 7.1.

All these change from baseline analyses will only include data while subjects are receiving double-blind study drug. Data will not be not included for visits after a histologic non-responder at Week 12 had received single-blind (to subject) APT-1011 3 mg BID in Part 2.

For the analysis of change from baseline in the number of dysphagia episodes (see section 16.2.1.5) and dysphagia free days, for each dose that meets the criterion for statistical significance on the primary efficacy outcome, a Wilcoxon Rank-Sum test will be used to test whether the reduction in the number of dysphagia episodes from baseline is larger for the APT-1011 dosing group compared to the control.

Holm's step-down procedure (Holm, 1979) will be used to control the overall Type I error at 0.05, where the number of doses considered for inferential testing is equal to the number of doses that meet statistical significance for the primary efficacy analysis.

Holm's step down procedure will be implemented as follows:

Let the number of APT-1011 doses that meet statistical significance in the primary efficacy analysis be represented by d (where d is between 1 and 4 inclusive for this study).

Perform the Wilcoxon-Rank Sum test for each of the d doses vs placebo and rank the resulting p-values in ascending order: $p_1 \le p_i \le p_d$

Author: Version Number: 3.0

Version Date: 06NOV2019

Template No.: CS_TP_BS016 Revision 5 Reference: CS_WI_BS005

Page 46 of 70

For each dose the hypothesis to be tested is:

 H_0 : $Ri(x) \leq R_0(x)$

H1: $Ri(x)>R_0(x)$

where $R_i(x)$ and $R_0(x)$ are the distribution functions for the reduction in number of dysphagia episodes for APT- 1011 dosing group i and placebo respectively.

Step 1: Test the dose with smallest p-value (p₁)

The hypothesis H_0 will be rejected if the one-sided p-value p_1 is $\leq 0.05/d$

Step 2: Test the dose with second smallest p-value (p₂)

The hypothesis H_0 will be rejected if the one-sided p-value p_2 is < 0.05/d-1

Step 3: Test the dose with third smallest p-value (p₃)

The hypothesis H_0 will be rejected if the one-sided p-value p_3 is < 0.05/d-2

Step 4: Test the dose with fourth smallest p-value (p₄)

The hypothesis H_0 will be rejected if the one-sided p-value p_4 is < 0.05/d-3

Note that depending on the value of d, not all of these steps may be required.

